1. SYNOPSIS

COMPOUNDS:

- Glu-NH-CO-NH-Lys-(Ahx)-[68Ga(HBED-CC)] (68Ga-PSMA)
- Bombesin receptor antagonist (68Ga-Bombesin)

Study number: PCa Restaging – PET/MR

TITLE: Phase II prospective monocentric study on prostate cancer restaging by using PET/MR with innovative radiotracers	
TRIAL LOCATION U.O. Medicina Nucleare, IRCCS Ospedale San Raffaele / PI: Prof.ssa [name]	
STUDY OBJECTIVE(S)	
Overall goal: To provide an innovative approach to restage patients with biochemical recurrence of prostate cancer by using hybrid PET/MR with innovative radiotracers (68Ga-PSMA and 68Ga-Bombesin)
 
Primary endpoint:
 
 - To evaluate the diagnostic accuracy of 68Ga-PSMA PET/MR to identify the site of recurrence in patients with biochemical relapse of PCa after primary treatment and comparison with the performances of 68Ga-Bombesin PET/MR 
Secondary endpoint
 
 - To correlate 68Ga-PSMA PET/MR and 68Ga-bombesin-PSMA PET/MR imaging with clinical and pathological features. - To evaluate the results of a lesion-targeted approach in terms of biochemical-recurrence-free survival and clinical recurrence-free survival. A particular effort will be made in order to identify patients that might benefit most from this approach in terms of predictors of both positive imaging findings as well as response to local treatment of metastatic sites with both surgery and radiation therapy.
STUDY DESIGN	
Prospective monocentric study, 60 total patients enrolled. Phase II, open, uncontrolled study.
 
After exclusion of patients with contraindications to PET/MR examinations (See inclusion/exclusion criteria), the 60 enrolled patients will be submitted to both 68Ga-PSMA PET/MR and 68Ga-bombesin PET/MR imaging at our Institution.
 
Each PET/MR study will have a duration of approximately 2 hours (including approximately 1 hour of waiting time and 1 hour of execution of 68Ga-PSMA or 68Ga-Bombesin PET/MR study). To correlate 68Ga-PSMA PET/MR and 68Ga-bombesin-PSMA PET/MR imaging with clinical and pathological features, the following variables will be tested:
 
 - Age - Pre-operative PSA - Pathological Gleason score - Pathological stage - Time to biochemical recurrence

	
- PSA slope - PSA doubling time
 
Patients with the diagnosis of local recurrence will be submitted to standard clinical work-up procedures.


STUDY POPULATION
 
Main selection criteria: Prostate cancer patients who experienced biochemical recurrence after primary treatment.
 
Total expected number of patients: 60
	
Inclusion criteria:
 
 1. Patients with histological proven diagnosis of prostate cancer. 2. Patients treated with radical therapy (RP or EBRT, with or without further adjuvant therapies), who present rising serum PSA values ≥ 0.2 ng/mL. 3. Age ≥ 18 years-old. 4. Willing to provide a signed informed consent. 
Exclusion criteria
 
 1. Age < 18 years-old. 2. Previous and/or concomitant androgen deprivation therapy will be excluded. 3. Any additional medical condition that may significantly interfere with study compliance. 4. Contraindications to MR study (i.e. Pacemaker)

INVESTIGATIONAL PRODUCT(S)
 
Formulation(s):
 
 1. Glu-NH-CO-NH-Lys-(Ahx)-[^{68}Ga(HBED-CC)] (^{68}Ga-PSMA) 
Route(s) of administration: intravenously
 
Dose regimen: 160 ± 50 MBq
 
 2. Bombesin receptor antagonist (^{68}Ga-Bombesin) 
Route(s) of administration: intravenously
 
Dose regimen: 140 ± 50 MBq
	

EFFICACY CRITERIA: ^{68}Ga-PSMA PET/MR and ^{68}Ga-Bombesin PET/MR findings will be assessed as follow :
 
 1) histology (when deemed necessary by the clinician as expected under the normal care pathway) obtained by echographically-guided biopsy in suspected local recurrence in the prostate lobe or during pelvic and/or extraperitoneal lymph node dissection in the event of suspected nodal recurrence 2) Clinical and laboratory data of the same patients (i.e. serum PSA assay) foreseen within the normal clinical work-up. 3) Conventional imaging modalities performed to assess disease status as part of the routine clinical work-up including CT, pelvic mp-MR, MR and bone scintigraphy. 4) A comparison between the two modalities will be also performed. 	

SAFETY CRITERIA: data concerning safety and the registration of adverse events will be collected.
	

STUDY PROCEDURES
 
Sixty consecutive patients with biochemical recurrence ($\text{PSA} \geq 0.2$ ng/ml), previously treated with radical prostatectomy for organ confined prostate cancer will be enrolled during the whole duration of the study (36 months). Patients with previous and/or concomitant androgen deprivation therapy will be excluded from enrolment.
 
All patients will undergo both ^{68}Ga-PSMA PET/MR and ^{68}Ga-Bombesin PET/MR imaging at San Raffaele Scientific Institute in two different days (> 48 hours between the two studies) and within one month one from the other; all clinical and pathological variables available at the time of PET/MR studies will be recorded for each patient. PET/MR results will be compared to other imaging procedures performed and available in the course of routinely work-up evaluation.
	

PATIENTS TREATMENT AND PROCEDURES
 
Treatment approach will be based on all available clinical and instrumental data, including ^{68}Ga-PSMA and ^{68}Ga-Bombesin PET/MR, evaluated during multidisciplinary sessions including expert Urologists, Nuclear Medicine and Radiologist physicians. Patients with local recurrence will be candidate to salvage radiation therapy (sRT).
	


Patients presenting only LN recurrence will be proposed to be submitted to salvage lymph node (LN) dissection (sLND) or sRT; alternatively, conventional androgen deprivation therapy will be performed in those patients who will not be willing to undergo secondary surgery or radiation therapy.
 
To assess the diagnostic accuracy of 68Ga-PSMA and 68Ga-Bombesin PET/MR, images will be validated with: 1) histology (when deemed necessary by the clinician as expected under the normal care pathway) obtained by echographically-guided biopsy in suspected local recurrence or during sLND in the event of suspected nodal recurrence; 2) biochemical response after tailored treatment in patients submitted to sRT for local or LN recurrence 3) conventional imaging modalities performed to assess disease status as part of the routine clinical work-up.
 
The validation procedures reported in point 1), 2) and 3) will be performed according the timing required by the routine clinical work-up of the patient and so they could be performed at any time during the course of the study.
 
68Ga-PSMA and 68Ga-Bombesin PET/MR will be correlated with available clinical and pathological features. To assess the impact of 68Ga-PSMA PET/MR and 68Ga-Bombesin PET/MR in changing patients' management, patients will be followed-up after the execution of PET/MR studies. Patients will be followed-up until the end of the study period.
	

STATISTICAL CONSIDERATIONS
	
The sample size was computed based on sensitivity analysis for PET/MR in predicting lymph node metastasis. Assuming an average prevalence of lymph node metastasis of 35%, a total sample size of 60 patients is sufficient for evaluating a sensitivity of 80% with an absolute precision of 18% (at 95% confident level).
 
8Ga-Bombesin PET/MRI and 68Ga-PSMA PET/MRI will be compared. Sixty patients treated with radical prostatectomy with biochemical recurrence of prostate cancer (PSA < 0.2 ng/ml and raising) will be evaluated and recruited in the study. They will be submitted to both 68Ga-PSMA PET/MR and 68Ga-bombesin PET/MR. Clinical and pathological variables will be recorded for each patient. The exact sites of recurrence as well as the size of all lesions will be recorded for all patients at both imaging procedures. A direct comparison between the two tracers will be performed using Chi-square test for categorical variables.
 
Univariable and multivariable logistic regression analyses will be used in order to identify the predictors of positive imaging at both 68Ga-PSMA PET/MR and 68Ga-bombesin PET/MR.
 
In patients with evidence of local recurrence submitted to salvage radiation therapy the biochemical response to radiotherapy will be used as confirmation of the positivity of imaging.
 
In patients with nodal only recurrence, a salvage pelvic and/or retroperitoneal lymph node dissection according to the site of the positive nodes will be proposed. For patients undergoing nodal dissection, a direct comparison between PET studies and histopathological examination in terms of site and size of the recurrent nodes will be performed. The performance characteristics of both 68Ga-PSMA PET/MR and 68Ga-bombesin PET/MR will be evaluated and compared through accuracy, sensitivity, specificity, positive and negative predictive value in a patient-based as well as in a lesion-based approach.
 
For the evaluation of the response to lesion-targeted treatments Kaplan-Meier analyses as well as univariable and multivariable Cox regression analyses will be performed.

DURATION OF STUDY PERIOD
	
Total duration of the study: 3 years.
 
Each patient will perform two PET/MRI studies in two different days. Each study will last

	approximately 2 hours (including approximately 1h of waiting time and 1 hour of execution of PET/MRI study). If available, patients will be followed up until the end of the study period.
--	--

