8. TREATMENTS

In addition to the execution of 68Ga-PSMA PET/MR and 68Ga-Bombesin PET/MR scans, all the other imaging procedures and treatment strategies performed will be in the course of routine work-up patient management.

68Ga-PSMA PET/MR and 68Ga-Bombesin PET/MR study:

Tracers synthesis will be performed in our Department following IMPD. 68Ga-PSMA PET/MR study will start 60 minutes after the administration of 160 ± 50 MBq of 68Ga-PSMA and 68Ga-Bombesin study will start 45 minutes after the administration of 140 ± 50 MBq of 68Ga-Bombesin. For both scans the following protocol will be applied:

- localizer MR scans to define the number of table positions (PET-FOV) to acquire (4-min/table position); specific attenuation correction and anatomical localization MR sequences at each PETFOV; pelvic multi-parametric MR protocol according to European Society of Urogenital Radiology (ESUR) guidelines.
Gadolinium-based paramagnetic contrast agent will be injected intravenously with a dose of 0.1mmol/kg and an injection rate of 4 ml/sec. The MR protocol may be modified according to specific clinical requirements.

- PET-acquisition will start from the mid-thigh to the base of the skull base to exploit the reduced ⁶⁸Ga-PSMA and ⁶⁸Ga-Bombesin ligand uptake in the urinary system after pre-scan voiding. Acquisition should proceed from the lower end of the axial field of view cranially in order to minimize misalignment for the urinary bladder which tends to fill up during the time of the examination. PET scans will be acquired in three-dimensional (3D) mode with an acquisition time of usually 2–4 min per bed position. Overall, PET coverage will be identical to the anatomical MR scan range.

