9. STUDY PROCEDURES

9.1 Efficacy

Positive PET/MR findings will be compared to :

- 1) histology (when deemed necessary by the clinician as expected under the normal care pathway) obtained by echographically-guided biopsy in suspected local recurrence in the prostate lobe or during pelvic and/or extraperitoneal lymph node dissection in the event of suspected nodal recurrence
- 2) Clinical and laboratory data of the same patients (i.e. serum PSA assay) foreseen within the normal clinical work-up.
- 3) Conventional imaging modalities performed to assess disease status as part of the routine clinical work-up including CT, pelvic mp-MR, MR and bone scintigraphy.
- 4) A comparison between the two modalities will be also performed.

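### Independence of the conventional-imaging validator from PET/MR is not assured: no section fixes the PET/MR call first or says whether the reference images are read without it

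*Combined protocol and SAP*

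**What the plan says.** The primary aim (Synopsis and section 5.2) is the diagnostic accuracy of 68Ga-PSMA PET/MR for the site of recurrence, compared with 68Ga-Bombesin PET/MR. The Synopsis (patients treatment and procedures) and section 6.1 name three validators: histology where the clinician needs it, biochemical response after salvage radiotherapy, and "conventional imaging modalities performed to assess disease status as part of the routine clinical work-up". Section 9.1 lists the modalities: "routine clinical work-up including CT, pelvic mp-MR, MR and bone scintigraphy".

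On who sees what, and when:

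- The Synopsis describes a "Phase II, open, uncontrolled study".
- "Treatment approach will be based on all available clinical and instrumental data", expressly including both PET/MR scans, and these data are "evaluated during multidisciplinary sessions including expert Urologists, Nuclear Medicine and Radiologist physicians". Section 6.1 repeats this.
- "PET/MR results will be compared to other imaging procedures performed and available in the course of routinely work-up evaluation".
- Validation follows the timing of routine care. Of the three validators the Synopsis says: "so they could be performed at any time during the course of the study".

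Sections 6.1, 8, 9.1 and 12.2 do not say who reads the conventional images as reference, whether that reader knows the PET/MR result, or when the PET/MR call becomes final.

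**The concern.** An accuracy estimate needs an index reading and a reference reading made without knowledge of each other. Here either order of events leaves a route for one to influence the other. If the CT, MR or bone scan follows PET/MR, its reader may know which site was positive. If it comes first, nothing stops the PET/MR reader from consulting it before making the call.

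Doubtful findings then tend to be settled in favour of agreement. A doubtful reference finding is called positive where PET/MR was positive and negative where it was not, so sensitivity and PPV both rise with no gain in true performance. The confidence interval does not reflect this. Analysts could not correct it later unless the state of knowledge at each reading had been recorded at the time.

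**Working it through.** **The plan's own figure.** The only design figure is the sample size in section 12.1. Node-positive patients needed: 1.96² × 0.80 × 0.20 / 0.18² = 18.97, so 19. Total: 19 / 0.35 = 54.3, so 55. With the planned 60, 60 × 0.35 = 21 node-positive patients give a half-width of 1.96 × √(0.16/21) = 17.1%, inside the stated 18%. The 60 is adequate for its stated purpose, and the present point does not rest on it.

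**What the text establishes.**

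1. Conventional imaging is a reference component for the primary aim (Synopsis, 6.1, 9.1).
2. Both PET/MR results are available to the treating team and evaluated with all other data (Synopsis, 6.1).
3. The order of PET/MR and conventional imaging is open (Synopsis).
4. Section 9.1 frames the comparison as starting from positive PET/MR findings.
5. No masking, locked call or separate reference reading is described.

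Points 1 to 5 permit review bias. They do not show that it occurs.

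**Illustration of size.** All inputs are assumed. Let u be the share of all discordant reference verdicts (false positives and false negatives alike) that are switched to agree with PET/MR. With sensitivity and PPV of 70%, take 70 true positives (TP), 30 false positives (FP) and 30 false negatives (FN). Then:

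- TP′ = TP + u·FP; FP′ = FP(1 − u); FN′ = FN(1 − u)
- PPV′ = TP′/(TP′ + FP′); Se′ = TP′/(TP′ + FN′)

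| u | TP′ | FP′ | FN′ | PPV′ | Se′ |
|---|---|---|---|---|---|
| 0 | 70 | 30 | 30 | 70% | 70% |
| 0.10 | 73 | 27 | 27 | 73% | 73% |
| 0.20 | 76 | 24 | 24 | 76% | 76% |
| 0.30 | 79 | 21 | 21 | 79% | 79% |

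The switched false positives must enter sensitivity as well as PPV. Leaving them out would give 70/94 = 74.5% at u = 0.20, which is inconsistent with the PPV on the same row.

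If only a share w of discordant verdicts rests on conventional imaging, replace u by w·u. With w = 0.50 and u from 0.10 to 0.30, w·u runs from 0.05 to 0.15, and both measures are 71.5% to 74.5%.

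**Check at the planning values.** Take 21 node-positive and 39 node-negative patients, true sensitivity 80%, assumed specificity 80% to 95%, assumed 25% to 100% of patients verified by conventional imaging, and 10% to 50% of their discordant verdicts switched. At the upper end TP = 16.8, FN = 4.2, FP = 39 × 0.20 = 7.8, and Se′ = (16.8 + 3.9)/(20.7 + 2.1) = 20.7/22.8 = 90.8%. At the lower end Se′ is 80.4%. The effect runs from negligible to about 11 points.

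**The case against.** The strongest reply is that the sentence about multidisciplinary sessions concerns treatment, while validation is described separately. That is correct. A reader might infer that this group reads or adjudicates the reference imaging; no section says so. A reader might also infer that the group already holds both PET/MR results when conventional scans are read. The timing is open, so some scans may pre-date PET/MR. What survives is that neither order is protected, because the PET/MR call is not locked and the reference reader's knowledge is not stated.

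It can also be said that conventional imaging is only one of three validators. For patients having nodal dissection, section 12.2 specifies direct comparison with histopathology, which is less exposed. For local recurrence treated with salvage radiotherapy it specifies biochemical response, which is not an image reading. This limits the scope, but the documents do not say how many patients or lesions will rest on conventional imaging alone.

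Finally, a reader might infer a tilt towards PSMA, because section 4 calls it one of the most successful PSMA radioligands and notes limited data for Bombesin. The same section also calls Bombesin promising and reports encouraging results. That readers would confirm PSMA-only lesions more readily is conjecture, and no weight is put on it.

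Pelvic mp-MR appears both among the reference modalities (9.1) and inside each PET/MR examination (section 8: "pelvic multi-parametric MR protocol according to European Society of Urogenital Radiology (ESUR) guidelines"). That overlap is a separate matter; resolving it would leave CT and bone scintigraphy as they are.

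**Conclusion.** The point holds in limited form. The plan does not assure that conventional imaging, as a validator for the primary aim, is independent of the PET/MR scans it validates. Apparent sensitivity and PPV may be inflated; the documents do not support saying that they are. The documents give no basis for a size. The range of 73% to 79% from a true 70% rests on assumed accuracy, on an assumed switch of 10% to 30% of all discordant verdicts, and on every such verdict being open to switching. It shrinks in proportion to the share verified by conventional imaging and vanishes if no verdict is switched. This is more than missing detail, because knowledge at the time of reading may be unrecoverable if it is not recorded then.

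**What to change.** In sections 6.1, 9.1 and 12.2, with the Synopsis matched:

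1. Enter and lock on the CRF the per-site call for each PET/MR scan before any reference result is opened and before the multidisciplinary session.
2. For each conventional imaging report used as a validator, record on the CRF whether PET/MR was known when it was issued.
3. Keep the planned main analysis, and add a sensitivity analysis that leaves out lesions whose only validator was conventional imaging read with PET/MR known.

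The main analysis should not be restricted to reports issued without PET/MR. That would require masked re-reads or would discard later follow-up imaging, and it would leave the sensitivity analysis nothing to exclude.

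The cost is one lock step, one CRF field and fewer verified lesions in the sensitivity analysis. No extra reader or procedure is needed, and clinical discussion in the sessions is unchanged.

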2. FLOW CHART

	T0	T1	T2*
Inclusion/exclusion criteria evaluation	X		
Informed consent administration	X		
68Ga-PSMA or 68Ga Bombesin PET/MR study		X	
68Ga-PSMA or 68Ga Bombesin PET/MR study			X

* ≥ 48 hours \leq 1 month from T1

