5.2 Primary and secondary specific aims

Primary aim

To evaluate the diagnostic accuracy of 68Ga-PSMA PET/MR to identify the site of recurrence in patients with biochemical relapse of PCa after primary treatment and comparison with the performances of 68Ga-Bombesin PET/MR

Secondary aims

- To correlate 68Ga-PSMA PET/MR and 68Ga-bombesin-PSMA PET/MR imaging with clinical and pathological features.
- To evaluate the results of a lesion-targeted approach in terms of biochemical-recurrence-free survival and clinical recurrence-free survival. A particular effort will be made in order to identify patients that might benefit most from this approach in terms of predictors of both positive imaging findings as well as response to local treatment of metastatic sites with both surgery and radiation therapy.

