6. STUDY DESIGN

6.1 Description of the protocol

Prospective monocentric study (Phase II study).

Sixty consecutive patients with biochemical recurrence (PSA \geq 0.2 ng/ml), previously treated with radical prostatectomy for organ confined prostate cancer will be enrolled; patients with previous and/or concomitant androgen deprivation therapy will be excluded from enrolment.

All patients will undergo both 68Ga-PSMA PET/MR and 68Ga-Bombesin PET/MR imaging at San Raffaele Scientific Institute in two different days; all clinical and pathological variables available at the time of PET/MR studies will be recorded for each patient.

PET/MR results will be compared to other imaging procedures performed and available in the course of routinely work-up evaluation. Treatment approach will be based on all available clinical and instrumental data, including 68Ga-PSMA and 68Ga-Bombesin PET/MR, evaluated during multidisciplinary sessions including expert Urologists, Nuclear Medicine and Radiologist physicians. Patients with local recurrence will be candidate to salvage radiation therapy (sRT). Patients presenting only LN recurrence will be proposed to be submitted to salvage lymph node (LN) dissection (sLND) or sRT; alternatively, conventional androgen deprivation therapy will be performed in those patients who will not be willing to undergo secondary surgery or radiation therapy.

To assess the diagnostic accuracy of 68Ga-PSMA and 68Ga-Bombesin PET/MR, images will be validated with: 1) histology (when deemed necessary by the clinician as expected under the normal care pathway) obtained by echographically-guided biopsy in suspected local recurrence or during sLND in the event of suspected nodal recurrence; 2) biochemical response after tailored treatment in patients submitted to sRT for local or LN recurrence 3) conventional imaging modalities performed to assess disease status as part of the routine clinical work-up. 68Ga-PSMA and 68Ga-Bombesin PET/MR will be

correlated with available clinical and pathological features. To assess the impact of 68Ga-PSMA PET/MR and 68Ga-Bombesin PET/MR in changing patients' management, patients will be followed-up after the execution of PET/MR studies. Patients will be followed-up until the end of the study period.

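### Scan order is unassigned and neither read is protected from the other, so the tracer comparison in the primary aim is open to bias

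*Combined protocol and SAP*

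**What the plan says.** The design is within-patient: "the 60 enrolled patients will be submitted to both 68Ga-PSMA PET/MR and 68Ga-bombesin PET/MR imaging at our Institution" (Section 1, Synopsis, Study design). The Synopsis puts the scans "in two different days (> 48 hours between the two studies) and within one month one from the other". The flow chart (Section 2) has the same entry, "68Ga-PSMA or 68Ga Bombesin PET/MR study", at T1 and at T2. Its footnote sets the minimum gap as at least 48 hours, whereas the Synopsis says more than 48 hours, a small wording difference to reconcile.

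The primary aim (Section 5.2) has two parts: the accuracy of 68Ga-PSMA PET/MR in finding the site of recurrence, and "comparison with the performances of 68Ga-Bombesin PET/MR". For the second part the Synopsis says: "A direct comparison between the two tracers will be performed using Chi-square test for categorical variables". Section 12.2 also names the Chi-square test. Neither place mentions scan order.

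The Synopsis calls the trial a "Phase II, open, uncontrolled study". Section 6.1 bases treatment on all available data, including both scans, "evaluated during multidisciplinary sessions including expert Urologists, Nuclear Medicine and Radiologist physicians". Section 8 applies the same acquisition protocol, including pelvic multiparametric MR, at both visits. The Synopsis allows the validation procedures to take place at any time during the study.

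No section says who reads the scans, what a reader may see, whether the two reads are separated, or when a read becomes final. No imaging manual is cited; the only attachments named are the two product dossiers (Section 8.1).

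**The concern.** In a paired comparison of two tracers, a difference can be put down to the tracer only if the two results were obtained on equal terms. Two features of this plan leave that open.

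First, either tracer may come first for any reason, so one of them could usually come second without departing from the protocol.

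Second, the reader of the second scan may already know where the first was positive, and sees the same anatomy on the same MR protocol. A doubtful focus may be called on the second scan because the first showed it. Histology, PSA response or follow-up imaging could also be known before a study read is final, since nothing fixes the sequence.

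What is at stake is the size, and possibly the sign, of the tracer difference. A read made with knowledge of the other scan cannot be made independent afterwards, so the safeguard has to be in place before reading starts.

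**Working it through.** **Is there a figure in the plan to reproduce?** None bears on this point. Section 12.1 sizes the trial on the sensitivity of a single test: 1.96² × 0.8 × 0.2 / 0.18² = 18.97 node-positive patients, and 18.97 / 0.35 = 54.2, so 55 in total. Sixty is therefore sufficient, as stated: 0.35 × 60 = 21 node-positive patients are expected, with a half-width of 1.96 × √(0.16/21) = 17.1 points. That calculation involves neither a tracer difference nor scan order.

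**Inputs for an illustration.** The documents give no sensitivity for 68Ga-Bombesin, no discordance rate and no rate at which calls carry over between reads. All of the following are assumptions:

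- True sensitivities are 80% (tracer A, the better) and 60% (tracer B). The 80% matches the planning value in Section 12.1; the 60% is chosen for illustration.
- The tracers' errors are independent among diseased patients.
- A share c of what is seen only on the first scan is also called on the second, with c = 25% or 50%.
- The first read is not revised after the second. Carry-over of false-positive calls is left out.

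**Formulas.**

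- Seen by A only: p₁₀ = 0.80 × 0.40 = 0.32.
- Seen by B only: p₀₁ = 0.60 × 0.20 = 0.12.
- True difference: 0.32 − 0.12 = 0.20.
- A first: observed A − B = p₁₀(1 − c) − p₀₁.
- B first: observed A − B = p₁₀ − p₀₁(1 − c).
- Balanced order: the mean of the two, which equals (p₁₀ − p₀₁)(1 − c/2).

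| Order | c = 0 | c = 25% | c = 50% |
|---|---|---|---|
| Better tracer first | 20 | 24 − 12 = 12 | 16 − 12 = 4 |
| Weaker tracer first | 20 | 32 − 9 = 23 | 32 − 6 = 26 |
| Balanced, reads unmasked | 20 | 17.5 | 15 |

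(Observed difference in percentage points.)

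**Equal tracers.** With both at 80%, p₁₀ = p₀₁ = 0.80 × 0.20 = 0.16. Carry-over then creates a difference of 0.16c, that is 4 points (c = 25%) or 8 points (c = 50%), in favour of whichever tracer is second. Balanced order returns zero.

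**Sensitivity to the independence assumption.** Suppose instead that everything B sees is also seen by A, so p₁₀ = 0.20 and p₀₁ = 0. With A first the difference shows as 20(1 − c) = 15 or 10 points. With B first it stays at 20. Balanced order again gives 17.5 or 15.

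**Reading the results.** Balancing the order removes the systematic advantage of being second, but does not stop a real difference from shrinking when reads are unmasked. Independent reads (c = 0) restore 20 points in any order under this model. The two safeguards address different parts of the problem.

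**The case against.** The strongest reply is that the protocol is silent on reading, and silence is not an instruction to read with the other scan in view. The multidisciplinary sessions decide treatment; nothing says they produce the study reads. The word open describes the trial design and does not by itself settle how images are read. Reading rules might exist in a manual or case report form that is not cited, and order might turn out balanced in practice. All of this stands as a limit on the claim: the plan permits the bias but does not show it. It does not answer the point, because the flow chart expressly allows either order and no section protects the reads. The gap of about 48 hours separates the scans, not the reader's knowledge.

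Three stronger readings are tempting, and the documents do not support them:

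- **That the comparison is already confounded.** Neither the actual order nor the actual reading practice is given.
- **That carry-over always makes the tracers look alike.** With the weaker tracer first and independent errors, the 20-point difference widens to 23 to 26.
- **That disease growth between scans favours the second tracer by a known amount.** The interval can be as short as about 48 hours, and nothing in the documents links time or PSA rise to lesion detection.

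It is also fair to object that the sample size rests on single-test sensitivity and that the accuracy of 68Ga-PSMA PET/MR against the reference standard is a separate part of the primary aim. This point concerns the comparison only.

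**Conclusion.** The point holds as a vulnerability in the design. Order is unassigned, reads are unprotected, and the exposed comparison belongs to the primary aim. The possible distortion is large relative to a plausible tracer difference: under the stated assumptions a true 20 points could appear as anything from 4 to 26, and two equal tracers could appear 4 to 8 points apart. These figures show direction and scale, not an estimate for this trial, because the sensitivity of the second tracer, the error dependence and the carry-over shares are all assumed. The result least dependent on the assumptions is that balanced order with unmasked reads shrinks a true difference by the factor 1 − c/2, whether errors are independent or nested. The change should be made because it is cheap and cannot be applied after the images have been read.

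**What to change.** 1. **Order.** Assign the tracer given at T1 from a pre-generated balanced random list of 60 lines. Record the order actually used, and report the paired comparison separately by order. Keep this descriptive: with about 21 node-positive patients expected, roughly 10 or 11 per order, a formal test for an order effect on nodal sensitivity would have little power.
2. **Reading.** Record the region-by-region result of each scan on the read form, then date and lock it before the other tracer's images, histology, PSA response or follow-up imaging are opened. If one reader reads both scans, use separate sessions.
3. **Disclosure.** Release the results to the multidisciplinary session only after the lock. The session then still has both scans.

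The cost is some loss of freedom in scheduling tracer production, which the documents do not allow to be sized, and a little reading logistics. No reader, scan or patient is added, and the planned sample size stays at 60.
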